2. BACKGROUND AND RATIONALE

3.1 Background and Scientific Rationale

Eosinophilic Esophagitis

EoE represents a complex clinical entity often requiring coordinated care within the fields of both allergy and gastroenterology. EoE is diagnostically defined by revised consensus criteria, that in brief require esophageal-specific inflammation of ≥ 15 eosinophils per high power field (hpf) as obtained from two to four biopsies from the esophagus, and that is not mitigated by the use of proton pump inhibitor (PPI) therapy¹. Symptomatically, patients with EoE often complain of dysphagia, vomiting, reflux, food aversion, and food impaction¹⁻³. These patients commonly have diagnoses associated with atopy and other allergic disorders such as IgE-mediated food allergy, asthma, allergic rhinoconjunctivitis, and eczema. Current treatment modalities focus on the use of the six food elimination diet (6FED), which consists of the empiric avoidance of the top 6 most common food allergens in the U.S. (milk, egg, wheat, soy, peanut/tree nuts, and fish/shellfish); implementation of a variety of directed elimination diets that rely on the use of allergy test results; the elimination of all antigenic proteins via the use of elemental formulas; or the use of swallowed steroid therapies (topical swallowed preparations of fluticasone or budesonide or oral systemic steroids)⁴⁻¹³. While all of these treatments are efficacious, they require continuous use or the disease will recrudescence in the majority of patients. Due to concerns about the risk of chronic topical swallowed steroid, patients and/or their families frequently opt to initially implement dietary therapy. This study is designed in keeping with this preference; therefore one of two empiric dietary therapies will be implemented initially prior to the use of topical swallowed steroids in participants who do not respond to the dietary treatment. The use of dietary restrictions as a treatment modality requires family and/or personal commitment to eliminating food, which may lead to significant nutritional deficiencies and is often life-altering.

3.2 Rationale for Selection of Investigational Product or Intervention

Current treatment modalities focus on the use of the six food elimination diet (6FED), which consists of the empiric avoidance of the top 6 most common food allergens in the U.S. (milk, egg, wheat, soy, peanut/tree nuts, and fish/shellfish); implementation of a variety of directed elimination diets that rely on the use of allergy test results; the elimination of all antigenic proteins via the use of elemental formulas; or the use of swallowed steroid therapies (topical swallowed preparations of fluticasone or budesonide or oral systemic steroids)⁴⁻¹³. While all of these treatments are efficacious, they require continuous use or the disease will recrudescence in the majority of patients.

Strictly adhering to any of these elimination diets is challenging for most patients, and so comparing response rates to a minimally restrictive therapy (1FED) against a more rigorous therapy (6FED) would be informative and potentially valuable.

It is considered standard of care for adults to undergo 6 weeks of dietary therapy, and studies have demonstrated that a 6-week trial of dietary therapy or even shorter for swallowed glucocorticoids is adequate for detecting change in disease status.^{58,59,31,21} Compliance is expected to be greater with a shorter therapy period as opposed to a longer one. It is also noted that the standard of care for children is to undergo 12 weeks of dietary therapy, at least in part because esophageal biopsies every 6 weeks may be a higher risk to children than biopsies every 12 weeks.

3.3 Preclinical Experience

3.3.1 Previous Research on the Use of Dietary Therapy in Eosinophilic Esophagitis

EoE is a chronic esophageal inflammatory disease typically triggered by exposure to food antigens. Given this, dietary elimination of these antigens has been tested as a therapeutic option. Previous work has shown that the exclusive use of elemental formula resulted in a response rate from 88-100% when histology and symptoms are considered, but difficulties with compliance, cost, and formula palatability have led to attempts to find alternative dietary approaches^{9, 13, 14}. Use of allergy testing to direct dietary elimination has been advocated, and in studies response rates from 53-77% have been reported. However, in practice the utility of allergy testing is very dependent on local expertise, and the response rate has been lower than hoped^{8, 13, 15}. Given this, there has been an attempt to use an empiric 6FED, which removes milk, soy, wheat, egg, peanuts/tree nuts, and fish/shellfish from the diet. This intervention has shown response rates ranging from 53-81% and is attractive due to the fact that no allergy testing is required. In all of these currently prescribed dietary therapies, the goal is to reintroduce foods systematically with subsequent endoscopy to try to identify specific causative antigens. A single small study of 17 children showed a partial or complete response rate of 65% using milk elimination alone¹⁶. In published reports where causative antigens have been identified, milk, wheat, and eggs have consistently been reported to be the top 3 offending food antigens^{8, 13, 17}. Strictly adhering to any of these elimination diets is challenging for most patients, and so comparing response rates to a minimally restrictive therapy (1FED) against a more rigorous therapy (6FED) would be informative and potentially valuable.

3.4 Clinical Studies

In a randomized controlled trial conducted by our group we assessed the efficacy of high dose fluticasone. Forty-two participants were enrolled in this study (28 FP, 14 placebo). After 3 months, 65% of FP-treated and 0% of placebo-treated participants had complete remission (P = 0.0001); 12% of FP-treated and 8% of placebo-treated

participants had partial remission. Of the FP-treated participants in complete remission, 73% continued in complete remission, and 20% were in partial remission after halving the daily FP dosage.⁵³ Vital signs and lab results were stable throughout the study. No participant was reported to exhibit clinical signs of adrenal insufficiency or glucocorticoid toxicity.⁵³

3. STUDY HYPOTHESES/OBJECTIVES

3.1 Hypotheses

We hypothesize that 6FED will be superior to 1FED, although we expect that a substantial (meaningful) percentage of patients will respond to 1FED.

We hypothesize that some patients who fail to respond to 1FED will respond to 6FED.

We hypothesize that some patients who fail to respond to 6FED will respond to SGC.

We hypothesize that HSS will more accurately quantify histological changes associated with EoE and be reversible following each therapeutic intervention. Furthermore, we hypothesize that some patients may show partial responses, where a subset of the HSS may be improved earlier or in dissociation with eosinophil levels, for example.

We hypothesize that molecular biomarkers will change (improve) with each treatment phase, at least in part. Furthermore, we hypothesize that biomarkers may reveal (a) novel insight into therapeutic resistance and/or relapse; (b) reveal patient sub-groups not identified by histology; and (c) ultimately prove to be readily usable biomarkers in clinical settings and possess personalized medicine value. If our hypotheses are proven to be correct, they have potential to transform monitoring of patients during therapeutic intervention, by identifying molecular markers that have therapeutic significance, and also by reducing the need for biopsies, particularly after therapy is initiated.

We hypothesize that the therapeutic interventions utilized in this study will improve clinical symptoms as measured by PRO metrics.

We hypothesize that certain patient phenotypes will correlate with response to each intervention in the trial.

We hypothesize that skin test results (prick testing to the 6 test foods and atopy patch testing to milk) will provide significant predictive value for outcomes in the diet trial phases.

3.2 Primary Objectives

To perform a prospective, randomized, non-blinded trial that determines the rate of remission following 1FED (milk elimination alone) vs. 6FED (milk, egg, wheat, soy, fish/shellfish, and peanut/tree nuts avoidance) and evaluates the relative efficacy of these dietary therapies (Phase 1).

The primary endpoint for this study will be the percent of participants who achieve histologic remission (<15 peak eosinophils/HPF) post therapy assessed after the end of the six week Phase 1.

3.3 Secondary Objective(s)

- To extend Phase 1 of this study with a prospective non-blinded trial that determines the rate of remission following SGC in the 6FED non-responders and the rate of remission following 6FED in the 1FED non-responders (Phase 2).
- To extend Phase 1 of this study with a prospective non-blinded trial that determines the rate of remission following 6FED in the 1FED non-responders (Phase 2).
- To evaluate the effect of each therapy on histological remission defined by a variety of changes in eosinophils, including (a) pre- and post-therapy peak eosinophil counts; (b) partial remission (2-14 peak eosinophils/hpf); and (c) complete histological remission (≤ 1 peak eosinophils/hpf).
- To evaluate the effect of each therapy by utilizing the histology scoring system (HSS) created to express the severity and extent of other abnormalities in the gastrointestinal (GI) tract that often accompany eosinophilic inflammation.
- To evaluate endoscopic outcomes as assessed by the endoscopy scoring system (EREFS).
- To determine the impact of each therapeutic intervention on biomarkers using the EoE Diagnostic Panel (EDP).
- To evaluate the clinical and psychosocial effect of each therapy utilizing surveys to assess EoE symptoms and problems/feelings related to eating.
- To determine if any clinical parameters predict response to therapeutic intervention.
- To determine if any biomarkers including serum food specific IgE, CRD, and IgG4 predict response to therapeutic intervention.
- To determine if skin testing, in the form of prick and patch testing, predicts response to therapeutic intervention.
- To determine if milk-driven T cells in the blood positively correlate with milk atopy patch test results and effectiveness of dietary therapies.
- To bank DNA so that we can later elucidate genetic components of EoE

4. STUDY DESIGN

4.1 Description of Study Design

We will be recruiting a total of 136 participants, between the ages of 18-60. Participants will be enrolled in this study based on the presence of active eosinophilic esophagitis and adherence to the inclusion and exclusion criteria.

[figure not shown]
We intend to conduct a prospective non-blinded randomized trial that compares a 1-food elimination diet (1FED) versus a 6-food elimination diet (6FED) for six weeks (Phase 1). Subsequently, non-responders to 1FED dietary elimination therapy will be treated with 6FED and non-responders to 6FED will be treated with SGC (swallowed fluticasone at a dose of 880 mcg twice a day) for six weeks (Phase 2) while on an unrestricted diet, if the participant chooses to continue in to Phase 2. The empiric dietary therapy interventions are as follows: 1-food elimination diet (1FED)—avoidance of milk vs. 6-food elimination diet (6FED)—avoidance of milk, egg, wheat, soy, fish/shellfish, and peanut/tree nuts, for six weeks. Milk elimination for both 1FED and 6FED includes all mammal milk (i.e. goat, sheep, and cow's milk must all be eliminated). The study design is shown schematically in Figure 1 Study Design Flowchart.

In Phase 1, all participants will be randomized 1:1 to either 1 food elimination (milk elimination alone, 1FED) or 6 food elimination (milk, egg, wheat, soy, fish/shellfish, peanut/tree nuts elimination, 6FED) therapeutic diet. At the end of this phase, an EGD will be performed to assess remission. Attainment of remission (esophageal eosinophil counts <15 eosinophils/high powered field) after Phase 1 will result in study discontinuation and maintenance of the “successful” dietary therapy. Treatment non-responders may choose whether or not to continue into Phase 2. Dietary therapy non-responders who were on 6FED in Phase 1 and continue in to Phase 2 will receive topical swallowed steroids for six weeks (Phase 2) followed by EGD with esophageal biopsies. These participants will return to an unrestricted diet (i.e. stop 6FED) prior to beginning topical swallowed steroid therapy. Dietary non-responders in Phase 1 who were on 1FED and continue in to Phase 2 will continue to a 6FED therapeutic diet (Phase 2) for six weeks followed by EGD with esophageal biopsies to assess remission.

The instructions for the 1FED and 6FED therapeutic diets will be standardized across sites by providing consensus documents produced by a central Registered Dietitian who is an expert in dietary elimination in EoE. There are currently no validated dietary questionnaires for measuring food allergen intake in adults in the US. Dietary intake and *consumption* of the allergens will be measured at the start of the trial and adherence to the dietary elimination (i.e. *avoidance* of the allergens) during the trial will be measured using modified versions of the NIC’s usual dietary intake/diet history questionnaires and food diaries from published pediatric EGID studies (<http://cancercontrol.cancer.gov>) and assisted by metabolomics. Stool samples may be collected from subjects who consent to stool collection to evaluate the effect of diet on the microbiome.

Similarly, standardized instructions for using SGC will be provided, based on our prior studies. We have chosen to use fluticasone propionate (FP) rather than budesonide in this study, given our prior work in this area, and our recent finding that high-dose fluticasone is well tolerated and highly effective, and our preliminary findings concerning esophageal transcripts that predict responsiveness to FP therapy. The study design is shown schematically in Figure 1 Study Design Flowchart.

Figure 1 Study Design Flowchart

4.2 Primary Endpoints

AIM 1: To determine the efficacy of a 1FED vs. 6FED in EoE.

- a. Primary end-point** The primary efficacy endpoint will be determined at the end of Phase 1 at which time all participants will undergo EGD with biopsy and the percentage of patients who have <15 peak eosinophils/hpf will be determined. The slides will be reviewed by local pathologists for clinical purposes, who will be blinded to the treatment group. The Central Review Pathology Committee (CRPC), who will also be blind to the treatment group, will also review the slides, and the peak eosinophil count from this CRPC review will be used to determine whether or not participants are eligible to continue into Phase 2 of the study. Participants with ≥ 15 peak eosinophils/hpf who were on 6FED during Phase 1 and choose to continue into Phase 2 will receive SGC for six weeks while on an unrestricted diet. Participants with ≥ 15 peak eosinophils/hpf who were on 1FED during Phase 1 and choose to continue into Phase 2 will maintain the 6FED therapeutic diet for 6 weeks. The CRPC will subsequently review the esophageal biopsy slides to determine other parameters (such as the Histology Scoring System (HSS)). CRPC review will be completed, whenever possible, within 2 weeks of a subject's endoscopy. Participants who achieve histologic remission at the end of Phase 1 (as determined by CRPC review) or who complete Phase 1 and opt out of Phase 2 will have completed the study and will resume follow-up care with their primary gastroenterologist or allergist.

4.3 Secondary Endpoints

Secondary end-point analysis: histology and endoscopy. Change in peak eosinophil count will be measured and we will also aim to determine the percentage of patients who achieve remission by more stringent requirements than the primary end-point, defined as both complete remission (≤ 1 peak eosinophils/HPF) and partial remission (< 10 and < 6 peak eosinophils/HPF) as reported⁶. This will allow us to compare with other studies that have used

6FED^{14,17,23,24}. Furthermore, we aim to more broadly examine the impact of each therapeutic intervention on other histological parameters associated with EoE using a quantitative histology scoring system (HSS) that has been developed by our expert pathologist, [name]. The HSS evaluates esophageal biopsies for various features (ex: basal layer hyperplasia, dilated intercellular spaces, surface epithelial alteration, apoptotic epithelial cells), eosinophilic inflammation (peak count, eosinophil abscess, eosinophil surface layering), and lamina propria (fibrosis). For central review, slides of relevant esophageal biopsies obtained during the course of the study will be scanned using an Aperio Imaging scanner and viewed by the CRPC using Aperio Imaging Software. Each member of the CRPC has access to an Aperio scanner in his or her pathology department and to the Aperio Imaging Software. Slides may be scanned into Aperio at the local site, or they may be sent to Cincinnati Children's Hospital Medical Center (CCHMC) to be scanned into Aperio (if the local site does not have an Aperio scanner). These slides will be returned to the local site once they have been scanned in. A password-protected website housing the scanned images will be created at CCHMC, and the CRPC will have access to that site. A secure image repository may also be housed at the Data Management Coordinating Center of the Rare Diseases Clinical Research Network at the University of South Florida. The CRPC will establish interobserver and intraobserver variability in their evaluation of eosinophils and other pathologic features: The central pathologists will re-count eosinophils in the scanned images of biopsies and compare the peak eosinophil counts that they obtained by viewing the scanned images to evaluate the variability in the counts. The CRPC pathologists will compare their results amongst themselves and resolve differences via teleconferences in which the scanned images are displayed (meetings hosted by GoToMeeting or equivalent sites). Ten percent intraobserver and interobserver variability will be considered optimum. Each review pathologist will review study slides from subjects enrolled at their own institution ([name], CCHMC; [name], CHCO; [name], NW). Relevant biopsy slides from the other participating sites will also be reviewed by the CRPC. The workload will be distributed as equally as possible among the CRPC pathologists with the assistance of the DMCC. Gastric and/or duodenal biopsies will only be reviewed by local clinical pathologists and will not be sent to the CRPC for review, except for cases where a participant's diagnosis is unclear (for example, when it is unclear whether a potential participant does or does not have eosinophilic gastritis or colitis). In such cases, the CRPC will review gastric and/or duodenal slides to confirm the appropriate diagnosis. Subjects may be included, without stomach or duodenal biopsies, if there is no clinical history of involvement of stomach or duodenum. We hypothesize that HSS will more accurately quantify changes associated with EoE and be reversible following each therapeutic intervention. Furthermore, we hypothesize that some patients may show partial responses, where a subset of the HSS may be improved earlier or in dissociation with eosinophil levels, for example. Finally, we will aim to determine the impact of the various therapeutic interventions on gross endoscopic changes, as determined by a recently developed endoscopy scoring system (EREFS) developed by [name] and colleagues²⁷.

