4.6 Stratification, Randomization, and Blinding/Masking

All eligible participants will be randomized 1:1 to either the 1FED or 6FED. Following this six week phase 1, all patients will undergo EGD with biopsy, and those whose disease remains active may choose to move on to Phase 2 (to either 6FED or treatment with swallowed SGC). The sponsor, investigator, study staff, and participant will all have knowledge of the treatment being received.

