6.5 Standard of Care Procedures Associated with This Study Esophagogastroduodenoscopy (EGD)

Endoscopy with biopsy is a well-established procedure. Few patients have unexpected or serious complications. Since it is considered standard of care for adult patients with EoE to have an EGD with biopsies within a six week time frame to monitor the disease when trialing new therapies (foods or medications), the EGDs with biopsies that are associated with this study are not study procedures. Endoscopies will be performed regardless of study participation as patients' standard of care, and additional endoscopic procedures will not be performed because of participation in this study. It is considered standard of care for biopsies to be collected from the esophagus, stomach, and duodenum during endoscopy, and biopsies from all of these sites will be collected during endoscopic procedures at all participating sites whenever possible. Biopsies collected from the stomach and duodenum are evaluated to determine study eligibility. Subjects may be included, without stomach or duodenal biopsies, if there is no clinical history of involvement of stomach or duodenum.

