13.3 Measures to Minimize Bias

Patients will be randomized using a 1:1 scheme to 1FED or 6FED within each investigative site. Study staff will remain blinded to the randomization plan so they do not know the upcoming treatment assignment will be for a patient until after the patient has been assigned. Study personnel who will perform the histologic assessments will be blinded to treatment assignment for the slides they are evaluating. The CRPC will not be told which diet a

participant has been assigned to, and they will not receive any information or documentation indicative of dietary assignment. The slides and/or images of slides provided to the CRPC will not contain any information that reveals which diet the participant is on. Knowledge of dietary assignment will be limited to study staff who need to know which diet a participant has been assigned to (i.e. dietitians).

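### Central pathologists are assigned their own institutions' slides for the primary endpoint; reading across institutions would remove an avoidable risk to the blind at almost no cost

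*Protocol*

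**What the plan says.** **Who decides the endpoint.** Protocol section 4.2 gives the end-of-Phase-1 decision to the CRPC. It describes those who finish the study as "Participants who achieve histologic remission at the end of Phase 1 (as determined by CRPC review". The SAP defines remission by the same cut-off of 15 eosinophils/hpf but does not name the reader.

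**Who reads which slides.** Section 4.3: "Each review pathologist will review study slides from subjects enrolled at their own institution". The three institutions are CCHMC, CHCO and NW. For the rest, "Relevant biopsy slides from the other participating sites will also be reviewed by the CRPC", with the workload shared out with the help of the Data Management and Coordinating Center (DMCC).

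**Safeguards.**
- Local readers (4.2): "The slides will be reviewed by local pathologists for clinical purposes, who will be blinded to the treatment group". The same section calls the CRPC blind.
- Central readers (13.3): "they will not receive any information or documentation indicative of dietary assignment". Slides and images are also to carry nothing that reveals the diet.
- Between readers (4.3): "The CRPC pathologists will compare their results amongst themselves and resolve differences via teleconferences in which the scanned images are displayed".

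**Who knows the diet.** Section 4.6: "The sponsor, investigator, study staff, and participant will all have knowledge of the treatment being received". Section 13.3 is narrower and limits that knowledge to staff who need it, such as dietitians.

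**Status of the endoscopies.** Section 6.5: "the EGDs with biopsies that are associated with this study are not study procedures". They are done as standard of care.

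**The concern.** Participants and site staff know the diet, so the masked histology count is the main protection for the primary endpoint. That endpoint is a manual peak count cut at one value. A small lean on slides near 15/hpf moves patients across the line, and the hypothesis in section 3.1 that 6FED is superior would give a lean its direction.

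The safeguards in 4.2 and 13.3 say that readers are blind and control what the study supplies to the CRPC. They do not say how a CRPC member is kept apart from clinical information in his or her own hospital. Section 4.3 places each member in a site pathology department, and section 4.2 has local pathologists read the same slides for clinical purposes. No rule stops one person from doing both reads, and no rule bars a member from local records. Removing labels from an image does not help if the reader already knows the case and its context.

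**Working it through.** **1. Does the plan close the route?** The relevant statements, side by side:

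| Point | What the protocol provides | What it leaves open |
|---|---|---|
| Material sent to the CRPC | Nothing indicating diet (13.3) | Knowledge reaching the reader by another route |
| Local clinical read | Stated as blinded (4.2) | Whether a CRPC member may also be the local reader |
| Local records | Not addressed | Whether a CRPC member may open them |
| Second look | Comparison and teleconference (4.3) | Whether every endpoint slide gets a second read from another institution |
| Staff who know the diet | 4.6 broad, 13.3 narrow | Which holds; 13.3 calls the histology assessors study personnel |

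The route is left open. The documents do not show that anyone has used it.

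**2. Check of the test.** The plan has no figure on this point, so its sample-size figure serves to check the calculation. With 60 per group, 45% against 70% and two-sided alpha 0.05 (section 13.6), exact enumeration of the likelihood-ratio test gives 80.6% power. This agrees with the stated minimum of 80%. The test stands in for the planned mixed model.

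**3. Size of the bias.** The documents give none of these inputs; all are assumptions:
- share of patients at the three institutions, *s*: 30% to 70%
- share of their slides close enough to 15/hpf to be called either way, *b*: 5% to 10%
- share of those moved when the diet is known: one half, in opposite directions in the two arms
- share of own-site reads for which the diet is known, *k*: 100% at first

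Bias in the remission difference = *s* × *b* × 0.5 × 2 × *k*

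- Low: 0.30 × 0.05 × 0.5 × 2 × 1 = 1.5 points
- High: 0.70 × 0.10 × 0.5 × 2 × 1 = 7 points

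With *k* lowered to 10% at the low end and 25% at the high end:
- 1.5 × 0.10 = 0.15 points
- 7 × 0.25 = 1.75 points

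**4. Effect on the error rate.** Exact rejection probability with 68 per arm, no true difference, and observed rates spread evenly around 45%:

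| Bias (points) | Two-sided error rate |
|---|---|
| 0 | 4.8% |
| 0.15 | 4.8% |
| 1.5 | 5.1% |
| 1.75 | 5.2% |
| 3 | 6.1% |
| 5 | 8.7% |
| 7 | 12.5% |

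**5. A second, milder scenario.** Assume a true rate of 57.5% in both arms (midway between 45% and 70%) and an own-site share of 33% to 75%. Assume also that 2% to 10% of 6FED non-remission reads at those sites are shifted to remission. Bias = share × shift × (1 − 0.575):
- Low: 0.333 × 0.02 × 0.425 = 0.3 points
- High: 0.75 × 0.10 × 0.425 = 3.2 points

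The error rate is 4.8% to 6.4%, against 4.7% with no bias.

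**The case against.** The strongest reply is that the plan is blinded as written. Local pathologists are to be blinded, so having read a slide clinically should not reveal the diet. The CRPC is to be sent nothing that indicates it, section 4.6 does not name pathologists among those who know, and readers compare counts and settle differences on shared images. Any harm requires the stated blind to fail at a particular reader.

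Most of this stands, and it limits the point. It does not remove it: section 4.3 does not say that each endpoint slide has a second read from another institution, and the blinding statements describe no separation inside the reader's own hospital.

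Three stronger readings are tempting, and the documents do not support them:
- *Diet is held in routine clinical records.* No section says so. It may be available there, but that is an inference from the endoscopies being standard of care.
- *The blind has failed, or is known to be weaker, at these three institutions.* Nothing shows this. The plan only forgoes a simple protection there.
- *Own-site reading spoils the independence of central from local reads.* No planned analysis uses that independence. Local counts serve clinical care and screening eligibility.

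The upper end of the bias range is also open to challenge. It takes the diet as known for every own-site read, which is the very point in doubt. The 70% enrolment share may be high, since two of the three institutions are children's hospitals by name and the trial enrols ages 18 to 60.

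**Conclusion.** The point holds as a cheap improvement to the protection of the primary endpoint. The own-institution rule is explicit, the CRPC count decides remission, and the protocol does not say how a reader is separated from local clinical information or from the local clinical read.

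The size runs from negligible to material, and the assumptions decide which. If the diet were known for all own-site reads, the error rate would be 5.1% to 12.5%. If it were known for 10% to 25% of them, the rate would hardly move from 4.8%. The documents do not let a reader choose between these cases. The reason to act is the low cost of removing the question, not evidence of bias.

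**What to change.** Replace the own-institution sentence in section 4.3 with a rule such as:

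*The DMCC assigns each scanned slide set, labelled with the study code only, to a CRPC member at another institution. A CRPC member who read a slide clinically does not give its central count.*

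Refer to this rule in section 13.3 as the means by which the central blind is kept. At the same time, reconcile sections 4.6 and 13.3 on who knows the diet.

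The cost is small. Section 4.3 already provides scanned images, a shared password-protected site, three readers and DMCC help with the workload, so no extra reader, biopsy or slide is needed. The downside is logistic: own-site slides must be uploaded and routed before they are read, within the 2-week target for CRPC review in section 4.2.

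If the reads are already done, record who read each slide and whether that person also read it clinically, and report own-site against cross-site reads. The re-counts of scanned images foreseen in section 4.3 could supply cross-site counts for slides from the three institutions.
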